**Table 1 : Proposal**

Title	A Randomised Controlled Trial of Intraoperative Cell Salvage during Caesarean section in women at risk of haemorrhage in China
Abbreviation	Cell Salvage during Caesarean Section- CSCS
Version	Version 2.1 dated 2016/2/12
Method	A randomized, controlled, single-blind and multi-centre clinical intervention trial with cost-effective analysis.
Trial Duration	2 years recruitment 6 months data analysis 6 months write dissertation (3 years in total)
Trial Center(s)	6 Centers of Obstetric who are eligible for clinical trials and are eligible for intraoperative cell salvage: 1. The Second Affiliated Hospital of Wenzhou Medical University 2. The First Affiliated Hospital of Wenzhou Medical University 3. Wenzhou People's Hospital 4. Taizhou Hospital of Zhejiang Province 5. Lishui City People's Hospital 6. The Central Hospital of Lishui City
Objectives	

• To determine the difference of blood loss postoperation in whether use of intraoperative cell salvage during caesarean section, or current practice of allogous transfusion.

• To look into and compare whether there is any adverse effects or reaction after IOCS or allogous transfusion.

• To determine if the routine use of IOCS during CS, in women at risk of haemorrhage, is cost effective in comparison to current practice.

Estimated number of subjects	120 cases

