#### 2.1.2 Secondary Objective

- PT/APTT, Hct and Hb in first and fifth day after surgery
- the number of units of donor blood transfused
- transfusion-related adverse reactions
- postoperative complications: amniotic fluid embolism, sepsis, acute respiratory distress syndrome, disseminated intravascular coagulation, wound infection, acute hemolysis, etc.
- mortality during hospital stay
- time to first mobilisation,
- duration of hospital stay
- intraoperative salvaged cell; before and after cesarean section, maternal's squamous epithelial cells, fetal red blood cells, serum potassium, free hemoglobin.
  - Before and after blood transfusion, maternal's electrolytes, PH value, fetal red blood cells, serum potassium, free hemoglobin
  - Total cost in hospital

Second Stage: Follow-up when pregnancy again:

- Neonatal hemolytic disease (Appendix 2)  
Determine blood type, antibody, and (Immunoglobulin G) IgG titer

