### 2.2 Study Design

A randomized, controlled, single-blind and multi-centre clinical trial with cost-effective analysis.

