#### 3.1 Eligible Criteria

##### 3.1.1 Inclusion Criteria

- 18 years of age or elder
- admitted to a participating labor ward
- delivery by elective or emergency caesarean section with an identifiable increased risk of haemorrhage
- ability to provide informed consent
- needing for blood transfusion during CS (according to blood transfusion guidelines [Appendix 1], obstetrician or anesthesiologist's advice)

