### 4.4 Randomization Process

Once subjects are confirmed through all the criteria and have received the informed

consent, they can be randomized to either the treatment group(Caesarean section with IOCS) or control group(Caesarean section without IOCS).The randomization will be proceed in operation if the patient needs blood transfusion.

Randomization (ratio:1:1) is used through a network-based randomization system, which follows SOP. We use central dynamic randomization system.

The randomization will be stratified by 5 conditions:

1. centers
2. type of cesarean section (Emergency/Elective)
3. whether there exist abnormality in placental
4. number of fetus (twins or more)
5. whether the ASA level is in I – II?

The randomization system will be tested and validated before the trial starts and will be supervised by the leader center's CRA and statistical expert throughout the trial. Once the subjects have been successfully grouped, they will be recorded in the enrollment form.

Each test center has their independent account and password for randomization system. The account number and password are authorized to the relevant staff by the major researchers in each center. After the staff has filled in the subject's ID and details into the randomization system, the system will display the grouping result.

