## 8.3 Statistical Methods

### 8.3.1 General Principle

Using SAS 9.13 for statistical analysis. All statistical tests should be two-sided. If p-value is less or equal to 0.05, then it is considered to be statistically significant.

Variables data are described by mean±standard deviation, median, maximum and minimum. Use paired t-test to compare intra-group variations with respect to baseline and use ANOVA or Wilcoxon rank-sum test to compare variations between groups.

Attributes data are described as frequency (percentage). Between group comparison of percentages is tested by Fisher's exact test

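### The economic objective is about routine IOCS in all at-risk women, but the trial contains only women who need transfusion and plans no analysis that pairs cost with an effect

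*Combined protocol and SAP*

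**What the plan says.** The third objective in Table 1 is "To determine if the routine use of IOCS during CS, in women at risk of haemorrhage, is cost effective in comparison to current practice". Section 2.2 describes the design as "A randomized, controlled, single-blind and multi-centre clinical trial with cost-effective analysis", and the Method row of Table 1 carries a similar label.

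The population is narrower. Besides an increased risk of haemorrhage, Table 1 and section 3.1.1 both require "needing for blood transfusion during CS". Section 4.4 states: "The randomization will be proceed in operation if the patient needs blood transfusion". Section 4.7 allocates women on haemoglobin triggers and staff judgement about transfusion, with donor blood as the example of control treatment.

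On the economic side, sections 2.1.2 and 8.2.2 list "Total cost in hospital", and the procedure table in section 4.8 records overall medical expenses once, at discharge. Section 8.3 has no passage on economic analysis. The only rule that could cover a cost variable is the general one in section 8.3.1: "use ANOVA or Wilcoxon rank-sum test to compare variations between groups".

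**The concern.** A routine-use policy is decided before anyone knows which women will bleed enough to need blood. Its cost includes collection equipment used for women who are never transfused, and its effect includes anything those women gain. A trial that starts from transfusion need sees neither. Followed as written, the plan gives a cost comparison between two ways of transfusing women who need blood, then reports it against a question about all at-risk women.

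The analysis has its own gap. A cost-effectiveness statement needs an incremental cost and an incremental effect. The plan names the cost, pairs it with nothing, and leaves open a test that does not target the mean. A payer's budget depends on the arithmetic mean cost per woman, and a rank test does not estimate a difference in means.

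**Working it through.** The plan gives no figure for the economic objective. Its only sample-size calculation (section 8.1.1) concerns blood loss, so there is nothing here to reproduce. The check is to compare what the objective needs with what the trial can observe.

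**Step 1: population.**

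| Element | Objective (Table 1) | Trial (Table 1 eligibility, 3.1.1, 4.4, 4.7) |
|---|---|---|
| Women | At risk of haemorrhage | At risk and needing transfusion during the operation |
| Strategy | Routine IOCS | IOCS once transfusion is needed |
| Comparator | Current practice across at-risk women | Donor blood in women who need blood |

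Section 4.3 conflicts with section 4.4: it places randomisation at preparation and states no transfusion condition. Section 3.2 also lists randomised women who no longer need a Caesarean section, which suggests randomisation before surgery. These passages must be reconciled, but they do not close the gap. Transfusion need remains an inclusion criterion, and section 3.2 treats a randomised woman who fails the inclusion criteria as a withdrawal.

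**Step 2: cost in the missing women.** Appendix 3 installs the suction tube, reservoir and heparin line first. The centrifuge cup is added when the transfusion indicator is reached or the doctor judges transfusion necessary. Under routine use, collection equipment would therefore be set up in women who never reach that point.

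**Step 3: what the objective needs.** Define:

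- p: share of at-risk women who need transfusion
- D: mean saving from IOCS per transfused woman, with set-up charged to IOCS
- C: collection set-up cost in a woman never transfused
- B: monetary value of any benefit of IOCS in such a woman

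If D carries over to routine use,

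net saving per at-risk woman = p × D + (1 − p) × (B − C).

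The trial can inform D only, which is the p = 100% case. The documents give no value for p, C, B or D, and no listed outcome or cost item supplies p, C or B.

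**Step 4: illustration on assumed values.** Assume B = 0. Break-even is then D/C = (1 − p)/p.

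| Assumed p | (1 − p)/p | D must exceed |
|---|---|---|
| 5% | 0.95/0.05 | 19 × C |
| 10% | 0.90/0.10 | 9 × C |
| 20% | 0.80/0.20 | 4 × C |
| 30% | 0.70/0.30 | 2.3 × C |
| 50% | 0.50/0.50 | 1 × C |
| 100% (trial) | 0/1 | 0 |

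A saving in transfused women could thus become a loss under routine use. If B is not zero, the second term is (1 − p)(B − C). Where B exceeds C it is positive, so routine use could look better than the trial result, and a loss in transfused women could become a gain. The sign depends on quantities the trial does not measure.

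**Step 5: analysis.** ANOVA compares arithmetic means and Wilcoxon compares ranks. Section 8.3.1 offers both, gives no rule for choosing and does not assign cost to either. The two can diverge when data are skewed. The documents show no cost data, but the pilot blood-loss figures in section 8.1.1 (mean 444, median 274, SD 709) show that skewed outcomes occur in this setting.

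**The case against.** The strongest reply is that one synopsis bullet is loosely worded and the rest of the document is modest. Section 1.2 says the study will compare the economic benefits of the two transfusion methods, which fits the randomised women. Effects that could be paired with cost are collected: donor units, length of stay, adverse reactions and blood loss. A cost-effectiveness analysis is announced, so its absence from section 8.3 could be called missing detail.

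Part of this stands. The data allow a cost comparison, and with an added plan a cost-effectiveness analysis, in women who need transfusion. But added detail in section 8.3 would not supply the missing women, so the Table 1 objective stays unanswerable until it is reworded.

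A reader might also infer three stronger points, which the documents do not support:

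- **A count of wasted sets.** With p assumed at 5% to 30%, 1/p gives 3.3 to 20 sets opened per woman transfused. The documents give no p and no set price. Under Appendix 3 a woman below the trigger uses the collection part and not the centrifuge cup, so this is not a count of full sets. Nor do they show which arm bears set-up cost: section 4.9.1 includes the recovery machine's volume in intraoperative blood loss without limiting it to one arm.
- **A certain bias towards IOCS.** This is plausible, because set-up cost in non-transfused women is left out. But sections 1.1 and 1.3.2 argue that salvage reduces postoperative anaemia and its consequences, and any such benefit in these women is left out too.
- **Costs will be analysed by ranks.** That criticism reaches only the Wilcoxon branch; ANOVA would compare means.

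**Conclusion.** The concern holds in this form: the plan as written cannot support a conclusion on the cost-effectiveness of routine IOCS in women at risk of haemorrhage. It can support a cost comparison between IOCS and donor blood in women who need transfusion, provided the mean difference is estimated. This rests on the plan's own eligibility and allocation text and needs no outside figure.

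The size and direction of any discrepancy between the trial result and routine use cannot be determined from the documents. The break-even multiples of 19 to 2.3 for p of 5% to 30% show only that a reversal is possible. They depend on an assumed p, on no benefit in non-transfused women, and on D carrying over to routine use. The objective is not the primary one, but as written it invites an economic claim for women the trial does not include.

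**What to change.** 1. Reword the Table 1 objective, and match the design label in section 2.2 and the Table 1 Method row. The objective becomes a comparison of cost, and of cost against a named effect already collected, between IOCS and donor blood in women who need transfusion during Caesarean section. This agrees with section 1.2.
2. Add to section 8.3 that cost is analysed as the difference in arithmetic means with a 95% confidence interval, for example by bootstrap, and not by a rank test.
3. Name the paired effect. Donor units are one available choice. Because allocation itself decides whether donor blood is the planned treatment, the report should say that the units difference partly reflects the design.
4. Label any statement on routine use in all at-risk women as a modelled scenario, with the transfusion rate and set-up cost given as external assumptions and varied over a range.

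The in-trial analysis needs no new patient data: the work is a wording change and a short analysis paragraph. The scenario needs outside inputs, since only overall expenses are recorded. The downside is a narrower economic claim.

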# Introduction

## 1.1 Background

Haemorrhage(excessive blood loss) is one of the major causes of maternal death. It is more likely to occur during caesarean section, especially for those maternal who have placenta accreta or placenta previa.

Blood is a scarce and expensive resource. Hospitals in China at all levels have varying degrees of tension with blood. Due to the scarcity of blood and maternal's risk of blood transfusions, it is common that mothers lose their blood transfusions in time, and result in postpartum anemia (low hemoglobin levels) in their mothers. A series of reports confirmed: anemia is a direct cause of maternal deaths. Life-threatening blood loss is an indication of emergency hysterectomy. A retrospective analysis involving 24 hospitals shows that at present, the total domestic cesarean section rate is 57.84% (2005 ~ 2006). Postoperative anemia will further prolong hospitalization, increase postoperative infection rates and delay the time of first mobilisation. Intraoperative cell salvage collects patients' own lost blood, wash and filter into the patient's own blood circulation. It may help to reduce the incidence of postoperative anemia for patients and avoid prolonged hospitalization. Although it has been confirmed that using cell salvage technology in some operations can reduce allogeneic blood transfusion, since clinical concerns about the amniotic fluid contamination of the blood transfused by the mother, intraoperative cell salvage during caesarean section has not yet been fully validated. At present, the National Institute of Health and Clinical Excellence has developed guidelines which recommend to use intraoperative cell salvage in the event of excessive haemorrhage in emergency cesarean section. In addition, intraoperative cell salvage is also recommended by the Royal College of Obstetricians and Gynecologists and the American Society of Anesthesiologists. At present, only a few clinical cases in China have been reported for washing autologous blood transfusion for maternal hemorrhage. No relevant randomized controlled studies were found in the literature. The risks of allogeneic blood transfusion include: death from transfusion errors, acute transfusion reactions, fatal lung injury and infections. Therefore, applying allogeneic blood transfusion to the healthy maternal need to be very cautious, and intraoperative cell salvage may possibly avoid these risks. Intraoperative cell salvage is a technique that can not only simultaneously reduce the need for allogeneic transfusions and prevent anemia, but also avoid bleeding-related serious complications. It has been shown to be well documented in non-cesarean sections, but current information is not able to demonstrate the safety and efficacy of autologous blood collection for bleeding during cesarean section, and have reported several cases of coagulation dysfunction associated with autologous blood collection. Therefore, it is necessary to carry out the monitoring of coagulation function and other checking of related

indexes for obstetric autologous blood transfusion patients . In addition, scientific rigorous test is necessarily to be carried out to demonstrate the safety and effectiveness of intraoperative cell salvage in cesarean section. We plan to construct a randomized controlled multicenter study to evaluate the safety and efficacy of intraoperative cell salvage in caesarean section, and provide some statistics for application of autologous blood transfusion in obstetrics.

## 1.2 CSCS

Intraoperative cell salvage collects patient's blood loss during surgery, and after separation purification and filtration, and then returns to the patient's own. This technique has been optimized in recent years, and it has been routinely used in departments which is at risk of heavy bleeding, such as cardiac surgery, orthopedics, hepatobiliary surgery and vascular surgery. British National Code of Practice is now only recommended to use of intraoperative cell salvage in the case of emergency cesarean section with heavy bleeding. However, in China, there's no guidelines recommending to use of intraoperative cell salvage in the case of cesarean section, but some hospitals in China have now tried to perform intraoperative cell salvage when lack of suitable allogenic blood. However, there's still a lack of evidence demonstrating the medical and economic benefits of intraoperative cell salvage for cesarean section. Regardless of amniotic fluid embolism, people generally think that intraoperative cell salvage technology may be superior to allogeneic blood. This protocol focuses on evaluating the difference in the efficacy of the two transfusion methods. In addition, this study will also compare the adverse reactions and economic benefits of two transfusion methods. Although currently the cost of intraoperative cell salvage is not low, compared with the cost of allogeneic blood transfusions and the extra cost of longer hospital stay and additional treatment, intraoperative cell salvage may reduce overall maternal medical costs.

## 1.3 Risk and Benefit of CSCS

### 1.3.1 Risk

As mentioned earlier, cesarean section has been considered a contraindication to the use of intraoperative cell salvage, due to the theoretical risk of amniotic fluid embolism(an extremely serious, but very low (about one in 200) incidence of pregnancy and maternal complications. However, with the update of technology (new filter equipment), this risk is theoretically even lower. After testing the mothers who has been used cell salvage in cesarean section, we found that after the modernization of equipments, those salvaged, purified and returned blood in cesarean section is the same

as the normal maternal blood.

In addition, during autologous blood transfusion, in theory, the contamination of fetal red blood cell may cause fetal hemolysis in another pregnancy, but there is no evidence that autologous blood transfusion can increase future fetal hemolytic disease.

About autologous blood transfusion and coagulation disorders, the general view is that autologous blood transfusion can wash out heparin and other anticoagulant substances, but there are also typical cases report that after autologous blood transfusion, abnormalities in coagulation index may happen. Since coagulation function and a variety of factors are related, in this trial, we will monitor some of the indicators.

The risks of allogeneic blood transfusions include death from transfusion errors, acute transfusion reactions, fatal lung injury, and transfusion infections.

Compared with the allogeneic transfusion group, there exists potential or undetected adverse events to subjects themselves.

### 1.3.2 Benefit

Intraoperative cell salvage may reduce the demand for allogeneic transfusions, and therefore less transfusion reaction and infection would happen than allogeneic transfusions. Postoperative anemia is related to the prolonged hospitalization, the increased wound infection and the delayed recovery of the patient's activity. Intraoperative cell salvage allows those original blood that may be discarded to go back to the patient, which greatly reduces the incidence of postoperative anemia.

## 1.4 Set-up

Prior to the protocol development, a systematic review of the literature has been conducted. Prior to the pretest, a series of surveys of maternal and obstetricians and anesthesiologists has been conducted as well to understand their acceptance of intraoperative cell salvage.

At the Second Affiliated Hospital of Wenzhou Medical University, we randomly invited 30 mothers to conduct a questionnaire survey. There are 29 successfully returned copies, and the response rate reached 96.7%. Data analysis shows that 75.86% of the mothers have some concerns on allogeneic blood transfusion, and 82.76% of the mothers have some concerns on intraoperative cell salvage. However, when mothers were asked, "if blood transfusion is needed during cesarean section, which method do you prefer?", 13.79% of mothers are willing to receive intraoperative cell salvage, 55.17% of mothers are willing to follow doctors' decision, and only 31.03% of mothers are willing to accept allogeneic blood transfusion only. And 24.14% of the mothers clearly declare that they are willing to participate in our trials. Therefore, during the trial, there was some difficulty in obtaining subjects' informed consent and joining the trial, but there was still a certain acceptance rate.

At the Second Affiliated Hospital of Wenzhou Medical University, we randomly invited 30 obstetricians to conduct a questionnaire survey. 29 of the surveys were successfully returned with a response rate of 96.7%. Data analysis shows that 89.66% of obstetricians were affected during their work due to blood difficulties. 89.66% of obstetricians have heard of intraoperative cell salvage, and 41.38% of obstetricians have used this technique in their work. 72.41% of obstetricians think autologous cell salvage is more beneficial than allogeneic blood transfusion, 27.59% of doctors are not sure which method is more favorable, but none of the doctors think that allogeneic cell salvage is more favorable than autologous blood recovery. Meanwhile, 100% of the doctors think it is necessary to have some research on the safety and efficacy of the two transfusion methods. When asking "if the mother needs blood transfusion during the cesarean section, are you willing to let the mother participate in this study", 48.28% of doctors are willing to, and 48.28% of doctors will be based on the condition. When asking the influence of postoperative bleeding according to the two transfusion methods, 68.97% of doctors are not sure about it. The above data not only show the good acceptance of autologous cell salvage from obstetricians, but also show the value of this trial.

At the Second Affiliated Hospital of Wenzhou Medical University, we randomly invited 30 anesthesiologists to conduct a questionnaire survey. All 30 of the surveys were successfully returned with a response rate of 100%. Data analysis shows that 76.67% of anesthesiologists were affected during their work due to blood difficulties. 26.67 % of anesthesiologists think autologous cell salvage is more beneficial than allogeneic blood transfusion, 66.67% of anesthesiologists are not sure which method is more favorable. The "uncertainty" is higher than obstetricians. Perhaps it is because anesthesiologists know more about intraoperative blood collection. When asking "if the mother needs blood transfusion during the cesarean section, are you willing to let the mother participate in this study", compared to obstetricians, there are also 48.28% of anesthesiologists would like to, and 48.28% of anesthesiologists will be based on the condition. When asking the influence of postoperative bleeding according to the two transfusion methods, compared to obstetricians, 68.97% of anesthesiologists are not sure about it.

